6 STUDY INTERVENTION

6.1 STUDY INTERVENTION

This is not a treatment study, so there is no treatment intervention. The study aims to assess feasibility of EMR-based outcome collection method, versus standard telephone collection method. The below descriptions refer to the experimental component of the study, in which the participants are randomized to one of two outcome assessment groups.

6.2 MEASURES TO MINIMIZE BIAS: RANDOMIZATION AND BLINDING

Subjects will be randomized to one of two outcome collection arms: EMR-based or telephone-based at the time of enrollment. Participants will be allocated to study group using fixed allocation randomization procedures, with a computer-based random number generating algorithm. Blocked randomization will be considered, with planned block sizes greater than the group number, and randomization will be stratified by mywakehealth enrollment status at the time of study consent. Outcome group assignment will not be blinded to the primary investigator or primary study coordinator, as it will be necessary for these individuals to know outcome assessment allocation in order for outcome collection to occur. When possible, outcome group assignment will not be shared with the epilepsy provider managing the participant, in an effort to reduce any potential bias in retention that could be introduced by the provider in clinical interactions with the participant.

7 STUDY INTERVENTION DISCONTINUATION AND PARTICIPANT DISCONTINUATION/WITHDRAWAL

7.1 PARTICIPANT DISCONTINUATION/WITHDRAWAL FROM THE STUDY

Participants are free to withdraw from participation in the study at any time upon request.

Although it is unlikely that a participant would need to be withdrawn from this study given its observational nature, the investigator may discontinue or withdraw a participant from the study for the following reasons:

- If any clinical adverse event (AE) or other medical condition or situation occurs such that continued participation in the study would not be in the best interest of the participant

The reason for participant discontinuation or withdrawal from the study will be recorded on the Discontinuation Case Report Form (CRF). Subjects who consent but are not randomized may be replaced. Subjects who consent, are randomized and receive instructions regarding the allocated outcome assessment arm, and subsequently withdraw, or are withdrawn or discontinued from the study may be replaced, but will also be included in outcome assessment unless the participant withdrew consent.

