3 OBJECTIVES AND ENDPOINTS

OBJECTIVES	ENDPOINTS	JUSTIFICATION FOR ENDPOINTS

Primary
 
To assess whether retention in the EMR-based outcome method arm at 6 months is sufficient in pilot testing to support use of this outcome assessment method in future pragmatic trials of management interventions for anxiety and depression in epilepsy.
	
-% retention in the EMR outcome arm, defined as the % of participants who complete the 6 month outcome instruments in the EMR
	
-obtain realistic estimate of feasibility of long-term EMR-based outcome assessment in this population

OBJECTIVES	ENDPOINTS	JUSTIFICATION FOR ENDPOINTS
Secondary		
To quantify retention at 3-and 6-months in the study population using a standard pragmatic trial outcome measure (telephone outcome assessment), and at 3 months using the EMR based outcome assessment method.	
-% retention at 6 months in the telephone outcome arm, defined as the % of participants who complete the 6 month outcome instruments via telephone
 
-% retention at 3 months in the EMR outcome arm, defined as the % of participants who complete the 6 month outcome instruments via telephone
 
-% retention at 3 months in the telephone outcome arm, defined as the % of participants who complete the 6 month outcome instruments via telephone
	
-to estimate future retention & develop retention strategy
 
-to assist in determining whether future studies should include telephone-or EMR-based outcome assessment for shorter and longer outcome assessment durations

To estimate 6-month change in epilepsy-specific quality of life (QOLIE-10, primary outcome) and depression and anxiety (secondary) at 3 and 6 months during usual care, among the feasibility cohort of individuals with epilepsy and borderline to high anxiety or depression scores at baseline.	
--6 month change in QOLIE-10 from baseline
 
--3 month change in QOLIE-10 from baseline
 
--change in anxiety (GAD-7) score from baseline to 3 and 6-month outcome assessments
 
--change in depression (NDDI-E) score from baseline to 3- and 6-month outcome assessments
	
-to generate preliminary estimates of effect for change in quality of life (and anxiety and depression) at 3- and 6-months from baseline during usual care, inputs that will be important for future trial planning with likely usual care control group

Tertiary/Exploratory		

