4 STUDY DESIGN

4.1 OVERALL DESIGN

This is a pilot pragmatic observational study of usual care quality-of life outcomes at 3- and 6-months among adults seen in a tertiary care epilepsy clinic. It is a feasibility pilot designed to specifically assess feasibility (retention) of a novel, EMR-based outcome assessment method among 30 adults with epilepsy and high or borderline anxiety and/or depression symptoms. Participants will be randomized 1:1 to either a traditional pragmatic outcome collection method (telephone interview) versus the EMR-based outcome assessment method. We will consider the EMR-based outcome assessment feasible if 60% of subjects in this arm are retained at 6 months. We will also assess retention in the telephone based outcome arm.

The 3- and 6-month outcome assessment instruments are brief and freely available measures amenable to future pragmatic trial use in outcome assessments (QOLIE-10, GAD-7, NDDI-E). Secondary objectives of the study include generating preliminary estimates of effect of usual care on quality of life outcomes (primary) as well as anxiety and depression outcomes (secondary).

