9.2 SAMPLE SIZE DETERMINATION

We are aiming to recruit 30 participants for the randomized outcome assessment feasibility study, with 15 in the EMR-outcome arm and equal allocation between EMR arm and the telephone arm. Using a

Bayesian design and a simulation study we assessed the probability of declaring acceptable adherence (80% credible interval that true adherence is at least 60%, $\Pr(X \geq 0.6) \geq 0.8$) over 10,000 simulated trials with sample size 15 in the intervention arm. We then summarized the results across all possible single trial outcomes and found if 11 to 15 subjects are retained, we are at least 83% confident that the true probability of retention is greater than 0.6. Thus, if at least 11 EMR arm participants meet the primary retention outcome, we will declare acceptable retention for using EMR based outcome assessment in future trials.

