9.3 POPULATIONS FOR ANALYSES

Intention to treat analysis will be carried out.

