9.4.2 ANALYSIS OF THE PRIMARY EFFICACY ENDPOINT(S)

The number of EMR-arm participants who meet retention criteria will be calculated, and as described above in the sample size determination section, if at least 11 EMR-arm participants meet the primary retention outcome, we will declare acceptable retention for using EMR based outcome assessment in future trials.

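### The go rule is a fixed count of 11 derived only for 15 EMR participants, but replacement after randomisation can raise the denominator, and 11 of 16 or more fails the plan's own 0.80 criterion

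*Combined protocol and SAP*

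**What the plan says.** - **Endpoint (section 3).** Retention in the EMR arm is a percentage, "defined as the % of participants who complete the 6 month outcome instruments in the EMR".
- **Derivation (9.2).** The plan has 30 randomised, "with 15 in the EMR-outcome arm and equal allocation between EMR arm and the telephone arm". Success means a posterior probability of at least 0.80 that true retention is at least 0.6. The simulation used 15 in the EMR arm, and the result is that "if 11 to 15 subjects are retained, we are at least 83% confident that the true probability of retention is greater than 0.6".
- **Decision (9.4.2).** "if at least 11 EMR-arm participants meet the primary retention outcome, we will declare acceptable retention". No threshold is given for any other arm size.
- **Replacement (7.1).** Participants who were randomised and instructed, and who then withdraw or are withdrawn, "may be replaced, but will also be included in outcome assessment unless the participant withdrew consent".
- **Loss to follow-up (7.2).** A participant who stays unreachable is treated as withdrawn.
- **Population (9.3).** "Intention to treat analysis will be carried out". Nothing is said about replaced participants.
- **Randomisation (6.2).** "Blocked randomization will be considered, with planned block sizes greater than the group number", stratified by patient-portal status.
- **Overall design (4.1).** "We will consider the EMR-based outcome assessment feasible if 60% of subjects in this arm are retained at 6 months".

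**The concern.** The endpoint is a proportion, but the decision is taken on a count that is valid for one denominator only. The EMR denominator can move away from 15 in two ways: a replacement is randomised to EMR while the withdrawn participant is still counted, or allocation is uneven because blocking is not committed to. Each extra participant is another chance to reach 11 while the bar stays where it was.

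Participants who withdraw consent raise the opposite problem. If they are dropped and replaced, the denominator returns to 15 and 11 of 15 passes, but only because randomised people who were not retained have been taken out of a retention endpoint. That sits badly with intention to treat.

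Section 4.1 also states feasibility as 60% retained, which is a lower bar than 11 of 15.

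At stake is the study's primary decision, whether EMR outcome assessment is used in future trials. The plan could declare acceptable retention when its own criterion fails on the people actually randomised, or give opposite answers from two sections on the same data.

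**Working it through.** **Inputs.** From 9.2: target 0.6, posterior bar 0.80, n = 15, threshold 11, stated confidence at least 83%. From 4.1: 60% retained. The prior is not stated, so a uniform Beta(1,1) is assumed, with Jeffreys Beta(0.5,0.5) alongside.

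**Formula.** With k retained of n and a uniform prior, Pr(p ≥ 0.6 | k, n) is the upper tail of Beta(1+k, 1+n−k) beyond 0.6. This equals Pr(Bin(n+1, 0.6) ≤ k).

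**1. Reproduce the plan's figure.** For 11 of 15: Pr(Bin(16, 0.6) ≤ 11) = 1 − 0.167 = 0.833. For 10 of 15 the result is 0.671. So 11 is the smallest passing count at n = 15, and the stated 83% is recovered.

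**2. Hold the count at 11 and let n grow.**

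| EMR n | Posterior, uniform | Posterior, Jeffreys | Pr(at least 11 retained) at true 0.60 |
|---|---|---|---|
| 15 | 0.833 | 0.855 | 0.217 |
| 16 | 0.736 | 0.759 | 0.329 |
| 17 | 0.626 | 0.648 | 0.448 |
| 18 | 0.512 | 0.532 | 0.563 |

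Across six priors tried, 11 of 16 gives 0.736 to 0.783, so it fails under each.

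**3. Smallest count meeting 0.80.**

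| EMR n | 14 | 15 | 16 | 17 | 18 |
|---|---|---|---|---|---|
| Uniform | 11 | 11 | 12 | 13 | 13 |
| Jeffreys | 10 | 11 | 12 | 12 | 13 |

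**4. Section 4.1 against 9.4.2.** 60% of 15 is 9. With 9 or 10 of 15 retained, 4.1 says feasible and 9.4.2 does not; the uniform posteriors are 0.473 and 0.671. At 60% true retention, Pr(at least 9 of 15) = 0.610 against Pr(at least 11 of 15) = 0.217. Also, 11/16, 11/17 and 11/18 (69%, 65%, 61%) meet 4.1 and fail the 9.2 criterion.

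**5. How often it could matter.** This needs rates the plan does not give, so the following are assumptions: 15 per arm at first; withdrawal of 5%, 10% or 15% in both arms; one round of replacement, re-randomised 1:1; true retention p among all randomised; 400,000 simulated trials. The table gives the share of go decisions (at least 11 retained) that fail the 0.80 criterion (uniform prior) when everyone randomised to EMR is in the denominator.

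| True p | All withdrawals replaced (5/10/15%) | Half replaced (5/10/15%) |
|---|---|---|
| 0.60 | 36/54/64% | 21/36/47% |
| 0.70 | 24/36/42% | 14/24/31% |
| 0.75 | 17/25/29% | 10/17/22% |
| 0.80 | 10/15/16% | 6/10/13% |

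With all replaced, the go probability at p = 0.60 is 0.298, 0.384 and 0.474, against 0.217 with no replacement.

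**6. Uneven allocation alone.** Simple 1:1 randomisation of 30 gives Pr(EMR ≥ 16) = 0.428. Blocks of 4 in two strata give exactly 16 with probability 1/6 to 1/4, depending on stratum sizes. Both schemes are assumed.

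**The case against.** The arithmetic is not in dispute. The case on the other side is about reach.

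- **The rule has an implied denominator.** 9.4.2 refers back to 9.2, which is built on 15. That is right, and the rule reads naturally as 11 of 15. But the plan says nothing for any other arm size, and 7.1 makes other sizes possible.
- **Exceeding 15 is conditional.** Replacement is permitted, not required; a replacement may go to the telephone arm; and the target of 30 randomised in 5.4 could be read as a cap. These points stand as limits on frequency. A cap would itself contradict 7.1.
- **Timing.** At 5 enrolled per month, 30 are in after about 6 months, just as the first 6-month assessments fall due. Replacing late losses would mean extending recruitment, which the simulation ignores. The synopsis allows up to 3 years, so extension is possible.
- **The simulated shares depend on counting consent withdrawals.** If every withdrawal is a consent withdrawal, is excluded under 7.1 and is replaced, the failing share drops to 16/18/15% at 60% true retention and to 2% or less at 80%. This stands. That reading, however, is the one that removes retention failures from the endpoint.
- **Meaning of outcome assessment in 7.1.** It could mean continued data collection, with 9.3 alone setting the denominator. Then everyone randomised counts, and the fixed 11 fails more readily.
- **4.1 may be a loose summary of the 60% benchmark.** Possibly, but it is worded as a decision rule.
- **One extra participant changes the decision only at exactly 11 retained.** True. At n = 16 that outcome has probability 0.16 at 60% true retention (0.329 − 0.167).

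**Conclusion.** The concern holds. The threshold of 11 is right for 15 EMR participants and wrong for 16 or more, under every prior tried. This part needs no assumption about withdrawal. The conflict between 4.1 and 9.4.2 at 9 or 10 of 15 needs neither replacement nor uneven allocation.

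The overall frequency is uncertain. It rests on assumed withdrawal rates, on how many withdrawals are replaced, and on whether consent withdrawals are counted. With everyone randomised to EMR counted, the share of go decisions failing the criterion runs from 6% (80% true retention, 5% withdrawal, half replaced) to 64% (60% true retention, 15% withdrawal, all replaced). The plan should be corrected because this is its primary decision rule.

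**What to change.** - **7.1 and 9.3:** put everyone randomised to EMR in the primary denominator and count any withdrawal, including withdrawal of consent, as not retained. For this endpoint, either do not replace after randomisation, or count both the withdrawn participant and any replacement randomised to EMR.
- **9.2 and 9.4.2:** state the prior and define a go as a posterior probability of at least 0.80 that retention is at least 0.6, at the actual EMR denominator. List the resulting minimum counts by arm size, as in step 3 of the working.
- **4.1:** replace the 60% statement with a cross-reference to that criterion, so that there is one feasibility rule.

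The cost is wording in five sections, with no extra patients or data. Reported retention may be slightly lower, and without replacement the quality-of-life sample may fall slightly below 30.

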7.2 LOST TO FOLLOW-UP

A participant will be considered lost to follow-up if he or she fails to complete the 6-month outcome assessment and is unable to be contacted by the study staff.

The following actions must be taken if a participant fails to complete an outcome assessment appointment:

- Study staff will attempt to contact the participant and reschedule the missed outcome assessment within <1 week and counsel the participant on the importance of maintaining the assigned visit schedule and ascertain if the participant wishes to and/or should continue in the study.
- Before a participant is deemed lost to follow-up, the investigator or designee will make every effort to regain contact with the participant (where possible, 5 telephone calls or electronic communications in the EMR as outlined above followed by up to 3 attempts by the alternative modality (following primary retention outcome assignment as described in recruitment and retention section) and, if necessary, a certified letter to the participant's last known mailing address or local equivalent methods). These contact attempts will be documented in the participant's study file.
- Should the participant continue to be unreachable, he or she will be considered to have withdrawn from the study with a primary reason of lost to follow-up.

8 STUDY ASSESSMENTS AND PROCEDURES

8.1 EFFICACY ASSESSMENTS

Screening Assessment

-NDDI-E, GAD-7, QOLIE-10³⁸

Implementation Monitoring:

RE-AIM framework measures

Feasibility assessments:

Enrollment/Baseline Assessments:

-accrual assessment

Retention: defined as outcomes collected via randomized modality within 1 week of the final of 5 scheduled reminders following outcome assessment due date (see recruitment and retention section for details of reminder process for each arm).

-6 month retention in EMR outcome arm

-6 month retention in the telephone outcome arm

-3 month retention in EMR and telephone outcome arms, respectively

Other feasibility assessments:

-# attempts to contact participants in each arm

-staff time for telephone outcome assessment/telephone contact attempts/preparing mailed survey packets vs staff time to send EMR surveys and electronic reminders

-time for participant completion of EMR surveys

-delay from survey delivery to completion by participant

Usual care outcome assessments (3 and 6 months):

- QOLIE-10
- NDDI-E
- GAD-7
- healthcare utilization (ED visits, hospitalizations)

Review of Clinical Chart: this will be done for preliminary eligibility assessment and for supplementary information on medications prescribed and health care utilization during the study period.

Health Insurance Portability and Accountability Act (HIPAA) rules, other relevant federal or state laws, and local institutional requirements will be followed, as applicable.

8.2 SAFETY AND OTHER ASSESSMENTS

Screening Assessments for Safety: in EMR/routine clinic visit

-NDDI-E validated passive suicidality question for safety³⁹: if score indicates potential risk of suicidality, the electronic record system will be triggered to alert the treating epilepsy provider to assess for possible suicidality. These individuals will be excluded from study participation.

Other Enrollment Assessments:

- demographics, medications, medical history (largely based on EMR review)
- brief past psychiatric treatment history interview

Outcome Assessments

3-month assessment

- NDDI-E (validated passive suicidality question for safety)

6-month assessment

- NDDI-E (validated passive suicidality question for safety)

Safety plan at outcome assessments:

-further assess for active suicidality if score on suicidal ideation question of NDDI-E is 3 or higher (using crisis procedures questions outlined in manual and Appendix A). This will be done immediately during telephone outcome assessments.

If an EMR outcome assessment results in a high-risk score on the NDDI-E, high priority alerts (red flag inbasket message or page to study pager) will be sent to study staff, and study staff will then call the participant at the first opportunity available, to assess need for any further action. All efforts will be made to send the EMR outcome assessment questionnaires at the start of a business day to allow maximal opportunity for rapid responses to occur during hours when study staff are available.

Participant emergency contacts may be called if the study staff is unable to reach the participant on the day that a high-risk score was identified. The proposed response time is faster than what may typically occur in standard care practice. For example, new patients to the epilepsy center receive a mailed version of the NDDI-E prior to initial visit, for completion, and these results which may be completed weeks before the visit are only reviewed by clinical staff at the time of the clinic visit.

Further details of safety protocol are outlined in section 8.5 and appendix A.

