- Multiple reminders and communications will be utilized to enhance participation in the outcome assessments. Telephone calls will be scheduled at the time of enrollment if possible. The outcome instruments will be mailed to telephone arm participants 10 days before scheduled outcome calls, and they will be sent electronically 10 days prior to target completion date for EMR-arm participants. Two telephone reminders for telephone arm participants, and two electronic reminders for EMR-arm participants will be provided prior to scheduled outcome assessment. Up to 5 attempts to call participants in the telephone outcome assessment arm will be made on separate days, starting at the originally scheduled outcome assessment time. Up to 5 electronic reminders with survey instructions will be sent via the EMR to the EMR arm participants, starting with target date for EMR outcome completion.
- After criteria for retention outcome at 6 months is met (5 reminders after due date for outcome assessment as described above), to reduce potential missing data for the secondary outcomes of 6-month change in quality of life, anxiety and depression, the following will be done. For any EMR-arm participants without successful 6-month outcome collection, 3 attempts will be made to collect outcomes via telephone. For any telephone arm participants without successful 6-month outcome collection, 3 attempts will be made to collect outcomes via EMR.
- Subjects will receive incentive of \$15 gift card for completing the brief baseline telephone interview and \$15 for completing each of the two outcome assessments (3 and 6 months).
- Efforts will be made to recruit any eligible participant seen in the practice, including women and under-represented populations

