Because this is not a treatment study, because we are excluding individuals with passive suicidal ideation at screening, and given the low rate of active suicidality we identified at baseline during our recent learning health system trial (included screening more than 760 individuals using the NDDI-E instrument), we anticipate that active suicidality will be exceedingly rare. All study staff will receive training on the crisis protocol and will have regular meetings with the team to discuss clinical issues.

Additional safety procedures for EMR outcome assessments

If in the EMR outcome assessment arm, a high score on the passive suicidality question of the NDDI-E will trigger an alert with high priority to study staff inbox and/or study team pager indicating that a high score was received.

The study team will call the participant as soon as feasible upon receiving the notification to assess for active suicidality and respond with further action as appropriate.

Staff will be instructed to follow the crisis protocol outlined in Appendix A and complete the Crisis Protocol Event Form. In both cases, the participant may be referred for psychiatric care by a physician or provider: their primary care physician, neurologist, APP, or emergency department physician.

Symptom Worsening

If there is significant symptom worsening at 3 month follow-up compared to baseline or at 6 month follow up compared to the prior assessment, a treatment resource handout will be mailed to the participant (see Appendix B). We will define treatment worsening as worsening in GAD-7 or NDDI-E score by 1 standard deviation^{12;32}.

Specifically, symptom worsening would be defined as the following:

- GAD-7 score increase of 5 points or more
- NDDI-E score increase of 4 points or more

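### A high-risk NDDI-E item 4 answer in the EMR may be alerted by inbasket alone, and the business-day safeguard times sending rather than answering

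*Combined protocol and SAP*

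**What the plan says.** Section 8.2 handles a high-risk NDDI-E score from an EMR assessment by alert: "high priority alerts (red flag inbasket message or page to study pager) will be sent to study staff". Section 8.5 says that a high score "will trigger an alert with high priority to study staff inbox and/or study team pager". Staff are then to ring the participant as early as they can. Section 8.2 also allows emergency contacts to be called if the participant is not reached on the day the score is identified.

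The timing safeguard is in 8.2: "All efforts will be made to send the EMR outcome assessment questionnaires at the start of a business day to allow maximal opportunity", and the sentence continues "for rapid responses to occur during hours when study staff are available". For the telephone mode, 8.2 says of the further suicidality assessment: "This will be done immediately during telephone outcome assessments".

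Section 5.4 sets the delivery schedule. For the EMR arm the instruments go out early: "they will be sent electronically 10 days prior to target completion date for EMR-arm participants". In addition, "two electronic reminders for EMR-arm participants will be provided prior to scheduled outcome assessment", and up to five more reminders follow from the target date. Section 8.1 counts an answer as retained until one week after the fifth.

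Section 8.5 gives participants crisis numbers and round-the-clock access to study staff or the on-call psychiatrist. For anything more, 8.2 points elsewhere: "Further details of safety protocol are outlined in section 8.5 and appendix A". It also cites a manual for the crisis questions.

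**The concern.** The safeguard acts on the wrong event. Sending a form early on a working day puts the answer in staffed hours only if the participant answers that same day. The schedule assumes that many will not: it sends the form well ahead and follows with up to seven reminders (2 + 5), and 8.1 records the delay between delivery and completion as a feasibility measure.

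For an answer given in the evening or at a weekend, what remains is the alert. If the alert is only an inbasket message, it does nothing until someone opens the inbasket. A team could then follow 8.2 and 8.5 to the letter and leave a score of 3 or 4 unread until the next working day. What is at stake is participant safety and the plan's own aim of a rapid response. The primary endpoint and the analysis are not affected.

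**Working it through.** The plan gives no figure to reproduce here, so the check is a reading of the text with some calendar arithmetic to show scale.

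**1. Does inbasket alone comply?** Section 8.2 joins the two channels with *or*; section 8.5 joins them with *and/or*. No sentence in either section requires the page. Inbasket alone complies, and so does a page.

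**2. Does the sending time fix the answering time?** The one stated length is the 10 days before the target date (5.4). Any 7 consecutive days contain a Saturday and a Sunday, so 10 days contain at least 2 weekend days as well as the nights. This needs no assumption.

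The full window is not stated, because reminder spacing is not given and the one-week tail in 8.1 is a rule for counting retention, not a portal closing time. Taking the tail as the end:

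- window = 10 + (4 × gap between the five reminders) + 7 days
- daily reminders (assumed): 10 + 4 + 7 = 21 days, holding 6 weekend days from any weekday start
- weekly reminders (assumed): 10 + 28 + 7 = 45 days, holding 12 to 14 weekend days

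These figures describe when the form is open. The documents give no distribution of answer times.

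**3. Do the other steps close the gap?**

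| Step | Section | What starts it |
|---|---|---|
| Staff call the participant | 8.2, 8.5 | Staff receiving the alert; no maximum time |
| Emergency contacts (optional) | 8.2 | Failure to reach the participant on the day the score is identified |
| 24-hour access, crisis numbers | 8.5 | The participant calling |

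None of these causes an unread alert to be read.

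**4. How long could a wait be?** Staff hours are not stated. Assuming weekday cover of 8 to 10 hours, an inbasket message arriving just after close would wait 24 − 10 = 14 to 24 − 8 = 16 hours overnight. Over a weekend it would wait 14 + 48 = 62 to 16 + 48 = 64 hours. This is an illustration under assumed hours, not an estimate for this trial.

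**5. How many forms?** Scheduled EMR questionnaires: 15 × 2 = 30. Section 5.4 also offers the EMR to telephone-arm participants who miss the 6-month call. That adds at most 15, and only if the whole telephone arm is missed. Replacement under 7.1 could add a few. How many of these would carry a score of 3 or 4 cannot be derived.

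**6. Which participants does the alert cover?** The alert sentence in 8.5 names the EMR arm. Its sub-heading and 8.2 refer to EMR outcome assessments generally, which takes in the telephone-arm fallback. This is a small mismatch of wording.

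**The case against.** The strongest reply is that the governing detail may lie elsewhere. Appendix A is described in 8.5 as covering the outcome assessments, and 8.2 also cites a manual. Out-of-hours handling would naturally sit there. This stands, and it limits the point to what 8.2 and 8.5 permit.

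The plan also has real protections. Item 4 scores of 3 or 4 are excluded at entry. Section 8.5 reports a low rate of active suicidality at baseline in a recent trial that screened more than 760 people. Participants receive safety instructions and crisis numbers, and emergency contacts are collected where possible. Section 8.2 argues that its response is faster than usual care, where a mailed NDDI-E can wait weeks for review. All of this bears on how often a wait would matter. It does not change when an alert is read, and the entry exclusion applies 3 and 6 months before the answers at issue.

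The contrast with the telephone is partly inherent: the caller is already on the line, and any questionnaire answered remotely brings delay. It is not evidence of a drafting error.

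Finally, a page helps only if someone carries the pager, and the amendment history (section 9.7, version 5) records that the system could not trigger one kind of alert. This also stands and shapes the fix.

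**Conclusion.** The point holds as a limited safety improvement. Sections 8.2 and 8.5 permit an inbasket-only alert, and the business-day measure does not govern when the answer arrives. Unless Appendix A or the manual adds cover, a high-risk answer given out of hours can wait until staff return. Such answers should be rare. Neither their number nor the length of the wait can be estimated from the documents, and the 21- and 45-day windows and the hours shown rest on stated assumptions.

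A reader might infer more than this, and the documents do not support it:

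- *That the trial has no out-of-hours cover.* Two cited sources are unseen, and 8.5 describes 24-hour access.
- *That alerts will go only to the inbasket.* The text equally allows the pager.
- *That telephone-arm participants who answer by EMR get no alert.* Section 8.2 covers any EMR outcome assessment.
- *That a participant is likely to be harmed.* No rate of high-risk answers is available.

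**What to change.** **(1) Portal notice, in any case.** Put on the EMR questionnaire: *Your answers are not read in real time. If you need help now, call the psychiatrist-on-call or the crisis hotline*, with the numbers that 8.5 already provides. This reaches the participant at the moment of answering. It costs one line on the form.

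**(2) Pager as well as inbasket.** In 8.2 and 8.5, replace *or* and *and/or* with: *Any NDDI-E item 4 score of 3 or 4 entered in the EMR by a participant in either arm, including telephone-arm fallback at 6 months, sends an alert to the study pager as well as the study inbasket.* Use the existing 24-hour arrangements, and check first that the system can page. This also removes the wording mismatch in 8.5. It costs a text change in two sections, a routing test and occasional out-of-hours pages.

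If the existing arrangements cannot cover the pager, only (1) applies. If Appendix A or the manual already gives out-of-hours cover, say so in 8.2 by cross-reference. What staff do clinically after an alert stays as Appendix A sets it.
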